to improve opioid management of primary care patients with chronic non-cancer pain. The stepped wedge cluster RCT design will allow us to examine the clinical impact of the intervention as the two components are implemented in a stepwise fashion across the health system. The EMR CDS guided care component went live across the health system as the standard of practice in October 2017. The stepped opioid CCM component will require 15 months to scale up in 3-month intervals across the health system. We will randomize the order in which stepped opioid CCM becomes available in each region. The study intervention targets primary care providers (Internal Medicine or Family Medicine) who are practicing in 35 clinic locations within 5 geographic regions of the Ochsner Health System. We will examine outcomes of care for their patients who meet the following inclusion criteria - age 18 and older, have a primary care provider at any of the study clinics, receiving opioid prescriptions (long-acting opioids or >3 months short-acting opioids) for chronic non-cancer pain, and have a diagnosis of depression or anxiety. Patient exclusion criteria include age <18 years, active cancer or undergoing cancer treatment, chronic cancer-related pain, having a terminal illness or receiving hospice care. We must accumulate healthcare data for 578 patients.

In **Aims 1 and 2**, we will compare the clinical effectiveness of electronic medical record-based clinical decision support (EMR CDS) versus additional integrated, stepped collaborative care (EMR CDS + stepped opioid CCM) and compare the cost effectiveness of the interventions. We hypothesize patients who receive additional stepped opioid CCM compared to EMR CDS guided care only will have greater decreases in total dosage of opioid medication prescribed. We also hypothesize that a higher proportion of patients who receive stepped opioid CCM will receive guideline concordant care, have greater reductions in inpatient hospitalizations and/or emergency department utilization and receive more cost-effective care. In **Aim 3**, we will conduct a qualitative assessment of the facilitators and barriers to implementing the multi-component intervention using the Consolidated Framework for Implementation Research. We hypothesize that intervention adaptability to local contexts, clinic readiness for implementation, and physician champions will influence implementation and subsequent performance of the intervention.

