### 1.4 Secondary

#### 1.4.1 Comparison of study groups

- Rate Ratio for average MEDD in post-index versus pre-index periods
- Inpatient hospital admission per 1000 patients
- Emergency Department visits per 1000 patients
- Odds Ratio for new post-index documented pain agreement
- Odds Ratio for new post-index documented urine drug screening
- Odds Ratio for new post-index documented naloxone prescription order
- Odds Ratio for new post-index documented referral to non-mental/non-behavioral health specialist
- Odds Ratio for new post-index documented anti-depression medications

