#### **5. Statistical Analysis**

Outcomes data were observed and collected in two time periods, pre-index and post-index. For the behavioral health group, the index date was defined as the date of enrollment during the study recruitment period (April 2019 to December 2021). For EMR-CDS usual care group, the index date is the first date within the study enrollment period at which a patient had been prescribed opioid medications for 90 of the previous 120 days.

Potential participants in the control arm of the study were identified from the chronic opioid health maintenance registry within the electronic health record system and propensity score matched to patients enrolled in the behavioral health arm. Baseline variables in the propensity score model were age at index event date, sex, race/ethnicity, average MEDD, anxiety, depression, and Charlson comorbidity index score. Average MEDD was calculated from opioid medication orders in the 12-month pre-index period. MEDD is calculated by determining the total daily amount of a prescribed opioid, multiplying the dose of the opioid by a conversion factor to ascertain morphine milligram equivalents and then adding up the converted dosage. Anxiety, depression, and Charlson comorbidity scores were determined from pre-index encounter diagnoses, historical problem lists, and PHQ-9/GAD-7 scores  $>10$  documented within the electronic health record.

Study outcomes were observed and collected in two 12-month time periods defined relative to the index date, pre-index and post-index, resulting in a 2-dimensional vector of repeated measures for each outcome from each patient. All outcome models for repeated measures incorporate a random effect with unstructured covariance matrix to model within-patient variability. It was assumed that patients remained in the health system from their first observed encounter through the end of the study period. A difference-in-difference approach was utilized in which outcomes were assessed as the change in group differences from pre- to post-

index. The model included fixed effects for study group, time (pre-index, post-index), and the group-by-time interaction.

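### With a fixed 12-month pre-index window and no look-back rule, earlier admissions and ED visits can be undercounted, which biases the between-arm utilization contrast if short histories differ by arm

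*SAP*

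**What the plan says.** On the outcome windows, SAP section 5 states: "Study outcomes were observed and collected in two 12-month time periods defined relative to the index date". On presence in the system it states: "It was assumed that patients remained in the health system from their first observed encounter through the end of the study period". Nothing is assumed about the time before that first encounter.

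The two arms have different index dates. For collaborative care it is the enrollment date, between April 2019 and December 2021. For usual care it is "the first date within the study enrollment period at which a patient had been prescribed opioid medications for 90 of the previous 120 days". Protocol C.1 asks for a primary care provider at a study clinic and either long-acting opioids or more than 3 months of short-acting opioids. Neither document, in the text available, asks for 12 months of prior record.

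The affected secondary outcomes in SAP 1.4.1 are inpatient admissions and "Emergency Department visits per 1000 patients", together with the first-time documentation outcomes. SAP section 5 analyses utilization with mixed negative binomial models containing group, time and their interaction, and names no offset. It analyses new documentation by logistic regression with a single group effect, among patients who had no such documentation before index. Protocol Table 1 (C.7.1) gives both EMR and claims as sources for admissions and ED use.

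**The concern.** The window is 12 months for everyone, but the entry rules allow a much shorter record. A control can qualify with about 3 to 4 months of prescribing, and a collaborative-care patient on long-acting opioids needs no minimum duration. If a patient's first encounter was 4 months before index, about 8 of the 12 pre-index months lie before the record starts. Unless claims fill that gap, or the model adjusts for it, those months are likely to enter as event-free. A partly observed year is then compared with a post-index year that the SAP assumes is fully observed.

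Two things are at stake. First, the utilization comparison in Hypothesis 1 rests on pre-to-post change, so an artificially low starting point looks like a rise. If more patients in one arm than in the other have short records, the difference-in-difference ratio moves away from 1 with no treatment effect. Second, a patient with a short record is more easily classed as never having had a pain agreement, urine drug screen or naloxone order, and so enters the group at risk of a new one. These models have no pre-index term that could absorb the problem.

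**Working it through.** The documents give no figure for time in system, share of short histories, or admission and ED rates, so there is no plan figure to reproduce. The calculation below is illustrative, and the shares and observed times in it are assumptions.

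**Set-up.** Let f be the share of an arm with a short history and q the mean fraction of the pre-index year observed in those patients. Assume a constant event rate and no capture of events before the first encounter. Then:

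- pre-index rate factor: k = 1 − f(1 − q)
- within-arm post/pre ratio under no change: 1/k
- ratio of rate ratios (collaborative care over control) under no effect: (1/k_I)/(1/k_C) = k_C/k_I

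**One affected patient.** With 90, 120 or 180 days observed, q is 90/365 = 0.25, 120/365 = 0.33 or 180/365 = 0.49. That patient's pre-index rate is 51% to 75% too low.

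**Within one arm.**

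| f | Months observed | k | 1/k |
|---|---|---|---|
| 5% | 6 | 0.975 | 1.03 |
| 10% | 6 | 0.950 | 1.05 |
| 20% | 6 | 0.900 | 1.11 |
| 20% | 3 | 0.850 | 1.18 |

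**Between arms.** Suppose first encounters are spread evenly over 90 to 365 days before index. Then q = (90 + 365)/2/365 = 0.623 and 1 − q = 0.377.

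- f = 30%: k = 1 − 0.30 × 0.377 = 0.887
- f = 5%: k = 1 − 0.05 × 0.377 = 0.981
- Controls 30%, collaborative care 5%: 0.887/0.981 = 0.90, an apparent benefit
- Shares reversed: 0.981/0.887 = 1.11, an apparent harm
- Equal shares: 1.00

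A milder contrast, with 6 months observed and shares of 20% in controls and 10% in collaborative care, gives 0.90/0.95 = 0.947. Reversed, it gives 1.056.

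**Could the shares differ?** Control index dates follow prescribing, while collaborative-care index dates follow referral or opt-in (Protocol C.4.4). The propensity model in SAP section 5 contains age, sex, race/ethnicity, average MEDD, anxiety, depression and Charlson score. It contains neither time in system nor prior utilization, so matching does not balance length of record directly. This makes a difference plausible but does not show one.

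**New documentation.** No size can be calculated, because the documents give no documentation rates. The problem is structural: eligibility depends on the absence of a prior entry, absence is easier to meet with a short record, and there is no pre-index comparison to subtract.

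**The case against.** The strongest reply is that the estimand is a difference-in-difference. A reader might infer that the undercount by itself biases the treatment comparison. It does not: with equal shares and equal observed time the no-effect ratio is exactly 1.00. This stands, and it limits the point to within-arm ratios, to differential histories, and to the new-documentation outcomes.

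A reader might also infer that controls are indexed when they start opioids or join the system. The SAP says the first qualifying date within the enrollment period, so a long-term user can be indexed near the start of that period with years of prior record. The 30% and 5% shares therefore have no source, and neither direction is favoured.

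It would also be too strong to say that no event before the first encounter can be recorded. Claims are a planned source for admissions and ED use and may recover some. Coverage is not stated, so how much they recover is unknown. Nor does the SAP say outright that time before the first encounter counts as event-free. Expressing rates per 1000 patients, with no offset named, points that way without settling it.

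Finally, the same presence assumption can undercount post-index events in patients who leave. If 10% leave with 6 months observed, the post-index factor is 0.95, which exactly offsets a pre-index undercount of the same size within an arm. That is a separate error. Chance cancellation does not correct either one, and a post-index censoring rule would leave the pre-index gap in place.

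**Conclusion.** The point holds in a limited form. The SAP combines a fixed 12-month pre-index window with presence assumed only from the first encounter, and the available text has no look-back rule or person-time offset. Where short histories exist and claims do not fill them, within-arm post/pre utilization ratios are inflated, by 1.03 to 1.18 over the assumed values tabulated. The ratio of rate ratios is biased only if short histories differ by arm. The illustrative size is 0.90 or 1.11 for 30% against 5%, and the true share and direction are not in the documents. The new-documentation outcomes are exposed to an extent that cannot be calculated.

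A reader might extend this to the primary outcome, MEDD of at least 50 mg, by supposing that a short record dilutes the 12-month average. The documents do not support that step. SAP section 5 derives average MEDD from medication orders and does not say which days form the denominator, so no effect on the primary outcome is shown.

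**What to change.** In SAP section 5:

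1. Report, by arm, the time from first encounter (or start of claims coverage) to index, and the share of patients with less than 12 months.
2. Repeat the utilization and new-documentation analyses in patients with at least 12 months of prior record. Apply the restriction in both arms before propensity matching, because several matching variables are themselves read from the pre-index record.
3. If all patients stay in the main utilization model, use log(observed pre-index days, capped at 365) as the pre-index offset. Start the clock after the first encounter and do not count an event that is itself the first encounter. Otherwise a patient whose only event is an ED visit at first encounter 120 days before index would score 1/(120/365) = 3.0 visits per year.

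The work is SAP wording plus one variable derived from encounter dates already held, with claims start dates where available. The price is the loss of some recent patients in the restricted analysis, which then describes a narrower group than Protocol C.1 admits, and slightly wider intervals. If short histories prove rare and balanced, item 1 will show it and the utilization results should change little.

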C.4.4. Patient Recruitment and Retention (Stepped Opioid CCM). All patient care received in the EMR CDS guided care arm of the study is per the discretion of patients' PCPs. Patients in the stepped opioid CCM arm of the study will be recruited by their PCPs who will refer them for care management. Patients may also self-refer by opting-in (i.e., contacting the research staff to express their interest in participating). To introduce the program to potential patients, the research team will send a mailing of the program flyer (i.e. BHI Team Flyer) and/or a MyOchsner notification (see Appendix A. Patient Self-Referral through MyChart). Individuals who receive the flyer or MyOchsner notification must contact the research team for more information. If the patient responds that they are not interested, they will be removed from further contact lists and instructed to let their PCP know if they change their mind about the program services.

All clinical services rendered will be incorporated into routine clinical operations which includes consent to treatment. All services provided by the CHW-LCSW-PharmD team members are grant funded. Therefore, patients will not be charged for services rendered. A variety of approaches will be used to retain patients including offering convenient options of telephonic and virtual visits (e.g. Ochsner Telemedicine MyChart video visits). Based on our experience, we understand the importance of creating a pleasant clinic environment and friendly and welcoming staff presence. We are also very clear from the initial screening session onward about what we expect from patients and what they can expect from us (including co-management and communication of care plans with their PCPs via the EMR). Keeping patients well informed enhances adherence to the intervention.

C.5. Aim 2: Cost Effectiveness of EMR CDS guided care versus additional stepped collaborative care

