For **Aims 1 and 2**, we will collect clinical and claims data to measure the main study outcomes (average morphine equivalent dose opioid prescriptions); and secondary outcomes (annual rates of service utilization; process of care measures; patient reported outcomes). . Specifically, Ochsner Information Analysts will export electronic medical records and claims data from the Enterprise Data Warehouse on a quarterly basis throughout the course of this study. Opioid prescription information from MedMined will be used as a data source. The analysts will upload data files onto a HIPAA-secure web-based file server. At the end of each study year, we will also administer a survey to assess changes in primary care physicians' attitudes and satisfaction with opioid management programming. For **Aim 3**, we will collect meeting minutes, emails, and conduct semi-structured interviews throughout the course of this study and comments physicians share via the annual survey.

Potential Risks. The risks for physical, psychological, social or legal harm are minimal from the present study. Specifically, we believe that the probability and magnitude of physical or psychological harm from enrollment in the present study is no more than that which is normally encountered in the daily lives of participants, or in the routine medical, dental, or psychological examination of healthy persons (45 CFR 46.303(d)). The primary risk for patients, staff, and providers participating in this study is the potential for having confidential information exposed, which will be minimized by following strict procedures as outlined below and by following any additional requirements as directed by the Ochsner IRB members.

Adequacy of Protection against Risks

Recruitment and Informed Consent.

We plan to request a waiver of **consent for participation in opioid management** and waiver of HIPAA authorization for extraction of clinical data from the enterprise warehouse.

For the **semi-structured interviews**, we are requesting a waiver of documentation of consent and will obtain verbal consent from interviewees volunteering to participate. The verbal consent to interview template is attached.

For the **online provider survey**, we also are requesting a waiver of documentation of consent. There will be a consent statement as follows: *By electronically submitting the survey, you are providing consent to participate. You are free to decline to answer any question you do not wish to answer.*

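### With one 12-month pre-index value per patient, the difference-in-differences can neither show nor correct a difference in dose trajectory between the groups before index

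*SAP*

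**What the plan says.** SAP section 5 reduces each repeated outcome to two values: "Study outcomes were observed and collected in two 12-month time periods defined relative to the index date". It describes the layout as "resulting in a 2-dimensional vector of repeated measures for each outcome from each patient". The model is equally compact: "The model included fixed effects for study group, time (pre-index, post-index), and the group-by-time interaction". For the primary outcome (SAP 1.3.1, average MEDD ≥50 mg) the effect is a ratio of odds ratios from a mixed logistic model. The approach is named outright: "A difference-in-difference approach was utilized in which outcomes were assessed as the change in group differences".

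Controls are drawn from the chronic opioid registry and propensity matched: "Baseline variables in the propensity score model were age at index event date, sex, race/ethnicity, average MEDD, anxiety, depression, and Charlson comorbidity index score". The dose variable in that list is a single number: "Average MEDD was calculated from opioid medication orders in the 12-month pre-index period".

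On entry to collaborative care, Protocol C.4.4 says: "Patients in the stepped opioid CCM arm of the study will be recruited by their PCPs who will refer them for care management". Opting in after a flyer or portal message is a second route. SAP section 5 indexes these patients at enrolment. It indexes controls at the first date in the enrolment period on which opioids had been prescribed for 90 of the preceding 120 days. Randomization (SAP section 3) set only the order of regional roll-out.

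Protocol Table 1 lists average daily dose as a quarterly measure, and under Sources of Materials analysts "will export electronic medical records and claims data from the Enterprise Data Warehouse on a quarterly basis". In the text available, neither document states a parallel-trends assumption, a pre-index check, a slope term or a sensitivity analysis for it.

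**The concern.** A two-period difference-in-differences estimates a programme effect only if, without the programme, both groups would have changed by the same amount. With one pre-index value per patient, the data as analysed contain nothing that bears on this. Matching on the 12-month mean aligns levels. It does not distinguish a patient whose dose fell through the year from one whose dose rose to the same mean.

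Unequal trajectories are plausible because the two index dates mark different kinds of event. One is enrolment in a service after a physician or patient decision. The other is the first date on which a prescribing-density criterion is met. A control who newly reaches that criterion has recently built up opioid supply, while an enrolling patient need not be at that point. Randomization does not protect the contrast, because patients were not randomized into the service.

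If trajectories do differ, the difference goes into the group-by-time term and nothing in the planned output would show it.

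**Working it through.** **Inputs.** From SAP section 4: 20% versus 10% with MEDD ≥50, odds ratio 2.25, 80% power, 245 per group. From SAP section 5: two adjacent 12-month windows. The differential trend d and the dose distribution in step 4 are assumptions, since the documents give neither.

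**1. The plan's own figures.** (0.20/0.80) / (0.10/0.90) = 2.25, usual care over collaborative care. At two-sided 0.05, the pooled log-odds-ratio formula gives a total of 376 against the stated 372. Then 372 × (1 + 10 × 0.03) = 483.6, rounded up to 35 × 14 = 490, and 245/0.85 = 288.2, so 289 per group and 578 in all. The plan's figures reproduce, the first to within about 1%.

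**2. How a trend enters.** The windows are centred at about −6 and +6 months. Suppose the groups agree exactly on the pre-index mean, the programme does nothing, and referred patients have an extra slope of b per month.
- Trend continues through the post-index year: shift = 12b = d, the yearly difference.
- Trend stops at index: shift = 6b = d/2.
- Trend shared by both groups: shift = 0.

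**3. Size on the odds-ratio scale**, starting from 20%:

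OR = 0.25 / [(0.20 − s)/(0.80 + s)], with s = d or d/2.

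| d (points a year) | Continues (s = d) | Stops at index (s = d/2) |
|---|---|---|
| 3 | 0.25/(0.17/0.83) = 1.22 | 0.25/(0.185/0.815) = 1.10 |
| 5 | 0.25/(0.15/0.85) = 1.42 | 0.25/(0.175/0.825) = 1.18 |
| 8 | 0.25/(0.12/0.88) = 1.83 | 0.25/(0.16/0.84) = 1.31 |

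These are marginal odds ratios. The SAP's mixed model estimates a patient-conditional ratio, which is on a different scale. A rise before index that continued would act in the opposite direction.

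**4. Would quarterly values help?** A simulation used 2,000 runs, 245 per group, eight quarters, no programme effect, flat controls and equal pre-index mean log dose. It assumed log-normal dose with median 25 and 20% at ≥50, and a within-patient quarterly SD of 0.3 on the log scale. For an extra fall that continues after index, the ratio of odds ratios (collaborative over usual care) and the false-positive rate for MEDD ≥50 were:
- none: 1.00, 5%
- 0.5% a month: 0.88, 15%
- 1% a month: 0.77, 47%
- 2% a month: 0.59, 94%

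If the fall stops at index, 1% and 2% a month give 16% and 47%. On the same data kept as quarters, a test of the pre-index slope difference in log dose detected 1% a month in 71% of runs and 2% in over 99%. A log-dose model with group-specific slopes returned a step ratio of 1.00 with about 5% rejections. The simulated test for the binary outcome was a marginal one, not the SAP's mixed model.

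**5. What a trend model costs.** Assume eight quarters, a linear trend and independent residuals with variance σ² after patient effects.
- Two-period contrast: variance (1/4 + 1/4)σ² = 0.5σ².
- One group-specific slope across both periods: the squared correlation of step and time is 24²/(378 × 2) = 0.762, so variance × 1/(1 − 0.762) = 4.2 and SE × 2.05.
- Pre-index slope projected forward 12 months: added variance 144/45 = 3.2σ², so 3.7/0.5 = 7.4 and SE × 2.72.

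If the two-period analysis has 80% power, these models have about 28% and 18%.

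**The case against.** The strongest reply is that nothing in the documents links referral to a change in dose. Protocol C.4.2 bases eligibility on PHQ-9 or GAD-7 scores, a depression or anxiety diagnosis, psychosocial concerns and chronic pain on opioids. Providers are notified through a registry with bulk orders, and opting in follows a mailing or portal message. None of these routes needs a taper or an escalation. This stands: a differential trend is possible, but it is not documented.

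A reader might go further than the documents allow in several ways:
- That patients are matched on average dose alone. The propensity score has seven variables. The narrower point is that average MEDD is the only one describing dose history.
- That any dose trend in referred patients will appear as an effect. Only a trend that differs from the controls' does so.
- That controls have no index trigger. They do, namely the prescribing criterion. The documented asymmetry is between two index rules.
- That quarterly pre-index doses have already been extracted. The Protocol's quarterly exports run during the study and do not by themselves show this. The firmer support is that the SAP already computes pre-index MEDD from individual orders.
- That an effect which loses significance in a trend-adjusted model should not be called causal. At the power in step 5, such a rule would withhold a true effect of the planned size in roughly 72% to 82% of trials.

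What survives is that the planned analysis cannot tell the reader whether the trajectories were parallel.

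**Conclusion.** The concern holds as an unprotected risk. With one pre-index value per patient and one dose-history variable in the matching, a differential pre-index trajectory would pass unseen into the primary ratio of odds ratios. It is tempting to conclude that the primary result is biased in favour of the programme. The documents do not support that, because they give no pre-index trajectory for either group. A fall in referred patients before index would exaggerate the benefit, and a rise that continued would hide it.

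The illustrative size is an odds ratio of 1.10 to 1.83 with no programme effect, against the planned 2.25. It rests on assumed differences of 3 to 8 points a year, on whether the trend outlasts the index date, and on a marginal scale. The simulated error rates depend further on an assumed dose distribution. The point merits a change to the SAP, mainly because the check is cheap.

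**What to change.** Make these changes in SAP section 5:
- From the medication orders already used for average MEDD, compute MEDD and the share ≥50 mg in each of the four pre-index quarters. Report both by group, with the group-by-quarter pre-index contrasts and 95% confidence intervals.
- Sensitivity analysis 1: repeat the matching with the four quarterly MEDD values in the propensity model, and re-estimate the primary outcome.
- Sensitivity analysis 2: fit a model with group-specific trends. Judge it by the shift in the estimate and its interval, not by loss of significance.
- State that the causal wording of the primary result will be qualified if pre-index trajectories differ materially.

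The SAP is written in the past tense. If outcomes have already been seen, both analyses should be dated and labelled as added. The primary matched cohort stays as it is.

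The cost is programming on existing orders. Some matches will be lost in analysis 1. The interval in analysis 2 will be much wider, with a standard error roughly 2 to 2.7 times as large under the assumptions in step 5, so on its own it can neither confirm nor refute the primary result.
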